### 5.12 Immunogenicity Analysis

The n count and % for each immunogenicity parameter will be summarized for all subjects in the Immunogenicity Analysis Set by treatment group.

Worldwide Clinical Trials Controlled Quality Management Document		
 WORLDWIDE CLINICAL TRIALS	Sponsor:	Eli Lilly and Company
	Protocol Number:	J4N-MC-YFAA
STATISTICAL ANALYSIS PLAN		

## 6 INTERIM ANALYSIS

There are no planned interim analyses for this study.

Worldwide Clinical Trials Controlled Quality Management Document		
 WORLDWIDE CLINICAL TRIALS	Sponsor:	Eli Lilly and Company
	Protocol Number:	J4N-MC-YFAA
STATISTICAL ANALYSIS PLAN		

## 7 DATA SAFETY MONITORING BOARD ANALYSIS

No data safety monitoring board (DSMB) analyses are planned.

Worldwide Clinical Trials Controlled Quality Management Document		
 WORLDWIDE CLINICAL TRIALS	Sponsor:	Eli Lilly and Company
	Protocol Number:	J4N-MC-YFAA
STATISTICAL ANALYSIS PLAN		

## 8 CHANGES TO PLANNED PROTOCOL ANALYSIS

There are no changes to the planned protocol analysis.

Worldwide Clinical Trials Controlled Quality Management Document		
 WORLDWIDE CLINICAL TRIALS	Sponsor:	Eli Lilly and Company
	Protocol Number:	J4N-MC-YFAA
STATISTICAL ANALYSIS PLAN		

## 10 LIST OF TABLES, FIGURES AND LISTINGS

The following table includes details of the tables, figures and listings to be included within each section of the eCTD. The eCTD section is shown in bold. The following validation methods maybe used:

- Independent programming of numbers and manual review of format (IP)
- Independent programming by statistician of numbers and manual review of format (Stat IP)
- Manual review (MR)
- Code review (CR)

Section Number	Table Number	Table Title	Validation Method	Shell Number (if repeat)
14.1.1	Participant Disposition			
	14.1.1.1	Participant Disposition, Part A – Screened Set	IP	-
	14.1.1.2	Screening Failures – All Participants	IP	-
14.1.2	Protocol Deviations			
	14.1.2.1	Protocol Deviations, Part A – Safety Analysis Set	IP	-
14.1.3	Demography, Baseline Characteristics, Treatment Compliance, and Analysis Sets			
	14.1.3.1	Analysis Sets, Part A – Screened Set	IP	-
	14.1.3.2	Demographics, Part A – Full Analysis Set	IP	-
	14.1.3.3.1	Previous Medical History by System Organ Class and Preferred Term, Part A – Full Analysis Set	IP	-
	14.1.3.3.2	Ongoing Medical History by System Organ Class and Preferred Term, Part A – Full Analysis Set	IP	14.1.3.3.1
14.3	Safety Data			
14.3.1	Adverse Events			
	14.3.1.1	Overall Summary of Treatment Emergent Adverse Events, Part A – Full Analysis Set	IP	-
	14.3.1.2	Treatment Emergent Adverse Events by System Organ Class and Preferred Term, Part A – Safety Analysis Set	IP	-
	14.3.1.3	Treatment-Related Treatment Emergent Adverse Events by System Organ Class and Preferred Term, Part A – Safety Analysis Set	IP	14.3.1.2

QMD Ref: Worldwide-TMP-ST-054-1.0_Effective: 12Aug2022	Governing QMD: Worldwide-SOP-ST-026
Confidentiality Statement This document is the property of Worldwide Clinical Trials Inc. and may not be duplicated, copied, altered or removed from company without prior approval from Worldwide Quality Assurance or in compliance with Worldwide Standard Operating Procedures.	

Worldwide Clinical Trials Controlled Quality Management Document		
 WORLDWIDE CLINICAL TRIALS	Sponsor:	Eli Lilly and Company
	Protocol Number:	J4N-MC-YFAA
STATISTICAL ANALYSIS PLAN		

Section Number	Table Number	Table Title	Validation Method	Shell Number (if repeat)
	14.3.1.4	Serious Treatment Emergent Adverse Events by System Organ Class and Preferred Term, Part A – Safety Analysis Set	IP	14.3.1.2
	14.3.1.5	Treatment Emergent Adverse Events Leading to Early Termination by System Organ Class and Preferred Term, Part A – Safety Analysis Set	IP	14.3.1.2
	13.3.1.6	Treatment Emergent Adverse Events by System Organ Class, Preferred Term and Maximum Severity, Part A – Safety Analysis Set	IP	-
	14.3.1.7	Treatment Emergent Adverse Events by System Organ Class, Preferred Term and Strongest Relationship, Part A – Safety Analysis Set	IP	-
14.3.2	Other Adverse Events			
	14.3.2.1	Listing of Deaths – Full Analysis Set	IP	(Listing) 16.2.7.1
	14.3.2.2	Listing of Serious Adverse Events – Full Analysis Set	IP	-
	14.3.2.3	Listing of Abnormal Laboratory Values – Safety Analysis Set	IP	-
14.3.4	Other			
	14.3.4.1	Vital Signs, Descriptive Statistics for Observed Values and Change from Baseline, Part A – Safety Analysis Set	IP	-
	14.3.4.3.1	Hematology Data, Descriptive Statistics for Observed Values and Change from Baseline, Part A – Safety Analysis Set	IP	-
	14.3.4.3.2	Hematology Data, Normal Range Shifts, Part A – Safety Analysis Set	IP	-
	14.3.4.4.1	Serum Chemistry Data, Descriptive Statistics for Observed Values and Change from Baseline, Part A – Safety Analysis Set	IP	14.3.4.3.1
	14.3.4.4.2	Serum Chemistry Data, Normal Range Shifts, Part A – Safety Analysis Set	IP	14.3.4.3.2
	14.3.4.5.1	Urinalysis Data, Descriptive Statistics for Observed Values and Change from Baseline, Part A – Safety Analysis Set	IP	-

QMD Ref: Worldwide-TMP-ST-054-1.0_Effective: 12Aug2022	Governing QMD: Worldwide-SOP-ST-026
Confidentiality Statement This document is the property of Worldwide Clinical Trials Inc. and may not be duplicated, copied, altered or removed from company without prior approval from Worldwide Quality Assurance or in compliance with Worldwide Standard Operating Procedures.	

Worldwide Clinical Trials Controlled Quality Management Document		
 WORLDWIDE CLINICAL TRIALS	Sponsor:	Eli Lilly and Company
	Protocol Number:	J4N-MC-YFAA
STATISTICAL ANALYSIS PLAN		

Section Number	Table Number	Table Title	Validation Method	Shell Number (if repeat)
	14.3.4.5.2	Urinalysis Data, Normal Range Shifts, Part A – Safety Analysis Set	IP	-
	14.3.4.6.1	Safety ECG Data, Descriptive Statistics for Observed Values and Change from Baseline, Part A – Safety Analysis Set	IP	-
	14.3.4.6.2	Safety ECG Data, Descriptive Statistics for QTcF Thresholds, Part A – Safety Analysis Set	IP	-
	14.3.4.6.3	Safety ECG Data, Overall Interpretation Shift from Baseline to Worst Post Baseline, Part A – Safety Analysis Set	IP	-
	14.3.4.7.1	Prior Medications by ATC Level 3 and Preferred Name, Part A – Full Analysis Set	IP	-
	14.3.4.7.2	Concomitant Medications by ATC Level 3 and Preferred Name, Part A – Full Analysis Set	IP	14.3.4.7.1
	14.3.4.8.1	PCSK9 Data, Descriptive Statistics for Observed Values and Change from Baseline, Part A – PD Analysis Set	IP	-
	14.3.4.8.2	Apo Panel Data, Descriptive Statistics for Observed Values and Change from Baseline, Part A – PD Analysis Set	IP	14.3.4.8.1
	14.3.4.8.3	CCI [REDACTED] [REDACTED] [REDACTED] – [REDACTED]	IP	14.3.4.8.1
	14.3.4.9	Linear Mixed-Effects Model for Plasma PK Concentrations of LY3885125 and ΔQTcF, Part A – PK Analysis Set	Stat IP	-
	14.3.4.10	Summary of Immunogenicity Parameters by Treatment Group – Immunogenicity Analysis Set	IP	-
14.4.1	PK Analysis			
	14.4.1	Descriptive Statistics for Concentration-Time Data of LY3885125 in Plasma after Single Ascending Subcutaneous Doses of LY3885125 – PK Analysis Set	IP	-

QMD Ref: Worldwide-TMP-ST-054-1.0_Effective: 12Aug2022	Governing QMD: Worldwide-SOP-ST-026
Confidentiality Statement This document is the property of Worldwide Clinical Trials Inc. and may not be duplicated, copied, altered or removed from company without prior approval from Worldwide Quality Assurance or in compliance with Worldwide Standard Operating Procedures.	

Worldwide Clinical Trials Controlled Quality Management Document		
 WORLDWIDE CLINICAL TRIALS	Sponsor:	Eli Lilly and Company
	Protocol Number:	J4N-MC-YFAA
STATISTICAL ANALYSIS PLAN		

Section Number	Table Number	Table Title	Validation Method	Shell Number (if repeat)
	14.4.2	LY3885125 Plasma Pharmacokinetic Parameters after Single Ascending Subcutaneous Doses of LY3885125 – PK Analysis Set	IP	-
	14.4.3	Amount of LY3885125 Excreted in Urine per Collection Interval – PK Analysis Set	IP	-
	14.4.4	Percentage of LY3885125 Dose Excreted in Urine per Collection Interval – PK Analysis Set	IP	-
	14.4.5	LY3885125 Urine Pharmacokinetic Parameters after Single Ascending Subcutaneous Doses of LY3885125 – PK Analysis Set	IP	-
	14.4.6	Dose-Proportionality Assessment of LY3885125 in Plasma after Single Ascending Subcutaneous Doses of LY3885125 – PK Analysis Set	MR	-

QMD Ref: Worldwide-TMP-ST-054-1.0_Effective: 12Aug2022	Governing QMD: Worldwide-SOP-ST-026
Confidentiality Statement This document is the property of Worldwide Clinical Trials Inc. and may not be duplicated, copied, altered or removed from company without prior approval from Worldwide Quality Assurance or in compliance with Worldwide Standard Operating Procedures.	

Worldwide Clinical Trials Controlled Quality Management Document		
 WORLDWIDE CLINICAL TRIALS	Sponsor:	Eli Lilly and Company
	Protocol Number:	J4N-MC-YFAA
STATISTICAL ANALYSIS PLAN		

Section Number	Figure Number	Figure Title	Validation Method	Shell Number (if repeat)
14.3.7	Other Safety			
	14.3.7.1	Scatter Plot of PK Concentration vs. QTcF – PK Analysis Set	IP	-
14.4	PK Analysis			
	14.4.1	Mean Plasma Concentration-Time Profiles of LY3885125 after Single Ascending Subcutaneous Doses of LY3885125 on Linear and Semi-logarithmic Scales – PK Analysis Set	MR	-
	14.4.2	All Subject Plasma Concentration-Time Profiles of LY3885125 after Single Ascending Subcutaneous Doses of LY3885125 on Linear and Semi-logarithmic Scales – PK Analysis Set	MR	-
	14.4.3	Plasma Concentration-Time Profiles for LY3885125 with Linear Regression for Estimating the Terminal Elimination Rate – PK Analysis Set	MR	-
	14.4.4	Assessment of LY3885125 C max vs. Dose – PK Analysis Set	MR	-
	14.4.5	Assessment of LY3885125 AUC last vs. Dose – PK Analysis Set	MR	14.4.4
	14.4.6	Assessment of LY3885125 AUC inf vs. Dose – PK Analysis Set	MR	14.4.4

QMD Ref: Worldwide-TMP-ST-054-1.0_Effective: 12Aug2022	Governing QMD: Worldwide-SOP-ST-026
Confidentiality Statement This document is the property of Worldwide Clinical Trials Inc. and may not be duplicated, copied, altered or removed from company without prior approval from Worldwide Quality Assurance or in compliance with Worldwide Standard Operating Procedures.	

Worldwide Clinical Trials Controlled Quality Management Document		
 WORLDWIDE CLINICAL TRIALS	Sponsor:	Eli Lilly and Company
	Protocol Number:	J4N-MC-YFAA
STATISTICAL ANALYSIS PLAN		

Section Number	Listing Number	Listing Title	Validation Method	Shell Number (if repeat)
16.2.1	Participant Disposition			
	16.2.1.1	Participant Disposition – Screened Set	IP	-
	16.2.1.2	Screen Failures		
16.2.2	Protocol Deviations			
	16.2.2.1	Protocol Deviations – Safety Analysis Set	IP	-
16.2.3	Demography, Baseline Characteristics, Treatment Compliance, and Analysis Sets			
	16.2.3.1	Analysis Sets – Screened Set	IP	-
	16.2.4.1	Demographics – Full Analysis Set	IP	-
	16.2.4.2	Previous Medical History – Full Analysis Set	IP	-
	16.2.4.3	Ongoing Medical History – Full Analysis Set	IP	-
	16.2.4.4	Prior Medications – Full Analysis Set	IP	-
	16.2.4.5	Concomitant Medications – Full Analysis Set	IP	-
	16.2.5.1	Dosing Information – Safety Analysis Set	IP	-
16.2.6	PK			
	16.2.6.1	Plasma LY3885125 Concentration Listing by Subject – Safety Analysis Set	MR	-
	16.2.6.2	Urine LY3885125 Concentration, Volume, Ae, and Fe% Listing by Subject and Collection Interval – Safety Analysis Set	MR	-
	16.2.6.3	Terminal Elimination Rate for LY3885125 for Individual Subjects – PK Analysis Set	MR	-
	16.2.6.4	Plasma PK Output Text – PK Analysis Set	MR	-
	16.2.6.5	Urine PK Output Text – PK Analysis Set	MR	-
	16.2.6.6	SAS Output Text for Dose Proportionality Assessment – PK Analysis Set	MR	-
16.2.7	Safety – Adverse Events			
	16.2.7.1	Adverse Events – Safety Analysis Set	IP	-

QMD Ref: Worldwide-TMP-ST-054-1.0_Effective: 12Aug2022	Governing QMD: Worldwide-SOP-ST-026
Confidentiality Statement This document is the property of Worldwide Clinical Trials Inc. and may not be duplicated, copied, altered or removed from company without prior approval from Worldwide Quality Assurance or in compliance with Worldwide Standard Operating Procedures.	

Worldwide Clinical Trials Controlled Quality Management Document		
 WORLDWIDE CLINICAL TRIALS	Sponsor:	Eli Lilly and Company
	Protocol Number:	J4N-MC-YFAA
STATISTICAL ANALYSIS PLAN		

Section Number	Listing Number	Listing Title	Validation Method	Shell Number (if repeat)
	16.2.7.2	Injection Site Reactions – Safety analysis Set	IP	-
	16.2.7.3	Hypersensitivity Laboratory Measurements – Safety Analysis Set	IP	-
16.2.8	Safety – Labs			
	16.2.8.1	Hematology – Safety Analysis Set	IP	-
	16.2.8.2	Serum Chemistry – Safety Analysis Set	IP	16.2.8.1
	16.2.8.3	Urinalysis – Safety Analysis Set	IP	-
16.2.8	Safety – Other			
	16.2.8.6	Vital Signs Data – Safety Analysis Set	IP	-
	16.2.8.7	ECG Data – Safety Analysis Set	IP	-
	16.2.8.9	Height and Weight Data – Safety Analysis Set	IP	-
	16.2.8.10	Pharmacodynamic Data – PD Analysis Set	IP	-
	16.2.8.11	Immunogenicity Data – Immunogenicity Analysis Set	IP	-

QMD Ref: Worldwide-TMP-ST-054-1.0_Effective: 12Aug2022	Governing QMD: Worldwide-SOP-ST-026

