#### 5.1.5 Pharmacokinetics (PK) Analysis Set

All participants who have received at least one dose of LY3885125 and have sufficient concentration-time data to estimate PK parameters.

The PK analysis set is used for the PK analyses.

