### 5.11.6 Electrocardiogram Data

Descriptive statistics for observed values and changes from baseline in the following ECG variables will be tabulated at each follow-up:

- Heart rate (bpm)
- PR interval (ms)
- QRS complex (ms)
- QT interval (ms)
- QTc interval (ms)
- QTcF interval (ms) [Fridericia's formula]
- QTcB interval (ms) [Bazett's formula]
- RR interval (ms)

QMD Ref: Worldwide-TMP-ST-054-1.0_Effective: 12Aug2022	Governing QMD: Worldwide-SOP-ST-026
Confidentiality Statement This document is the property of Worldwide Clinical Trials Inc. and may not be duplicated, copied, altered or removed from company without prior approval from Worldwide Quality Assurance or in compliance with Worldwide Standard Operating Procedures.	

Worldwide Clinical Trials Controlled Quality Management Document		
 WORLDWIDE CLINICAL TRIALS	Sponsor:	Eli Lilly and Company
	Protocol Number:	J4N-MC-YFAA
STATISTICAL ANALYSIS PLAN		

Number and percentage of subjects that meet each of the following categories will be presented:

- Largest postdose assessment of QTcF > 450
- Largest postdose assessment of QTcF > 480
- Largest postdose assessment of QTcF > 500
- Largest QTcF change from baseline > 30
- Largest QTcF change from baseline >60

Shift tables in relation to the overall interpretation (Normal; Abnormal Not Clinically Significant [NCS], and Abnormal Clinically Significant [CS]) from baseline to each follow-up visit will be presented.

The relationship between plasma PK concentrations of LY3885125 and  $\Delta$ QTcF will be quantified using a linear mixed-effects modelling approach. The model will have  $\Delta$ QTcF as the dependent variable, plasma PK concentrations of LY3885125 as the explanatory variate (0 for placebo), baseline QTcF as an additional covariate, study treatment (active = 1 or placebo = 0) and time (i.e., post-dose time point: categorical) as fixed effects, and random effects on intercept and slope per participant. In all calculations, concentrations in participants who received placebo will be set to zero. LY3885125 plasma PK concentrations below the quantifiable limit at pre-dose will be set to zero and after dosing will be set to 1/2 the lower limit of quantitation in the concentration-QTc analysis.

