An unstructured covariance matrix will be specified for the random effects. If convergence cannot be achieved even after appropriate rescaling of the concentrations, the random effect on the slope and intercept will be dropped, in this order, until convergence is achieved. The degrees of freedom (df) estimates will be determined by the Kenward-Roger method. From the model, the slope (i.e., the regression parameter for the concentration) and the treatment effect-specific intercept (defined as the difference between active and placebo) will be estimated together with the 2-sided 90% CI. The estimates for the time effects will be reported with standard error (SE).

The following SAS codes can be used to conduct the LME model in the example:

```
proc mixed data=PKQTc method=reml;
  class USUBJID AVISTPT;
  model  $\Delta$ QTcF=PRTAN CONC1 AVISTPT CBASE / solution cl noint alpha=0.1
    alphap=0.1 covb ddfm=kr;
  random int CONC1 / type=un subject=USUBJID s;
run;
```

Throughout the LME modelling, for any timepoints where triplicate values are collected for QTcF, then the arithmetic average of the triplicates should be analysed.

QMD Ref: Worldwide-TMP-ST-054-1.0_Effective: 12Aug2022	Governing QMD: Worldwide-SOP-ST-026
Confidentiality Statement	
This document is the property of Worldwide Clinical Trials Inc. and may not be duplicated, copied, altered or removed from company without prior approval from Worldwide Quality Assurance or in compliance with Worldwide Standard Operating Procedures.	

Worldwide Clinical Trials Controlled Quality Management Document		
 WORLDWIDE CLINICAL TRIALS	Sponsor:	Eli Lilly and Company
	Protocol Number:	J4N-MC-YFAA
STATISTICAL ANALYSIS PLAN		

A scatter plot of QTcF data vs LY3885125 plasma PK concentration will also be presented for all timepoints where an ECG and PK sample were drawn within the same 10 minute window, with unique formatting for each treatment group.

All ECG data, including details of any abnormalities, will be listed.

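### The concentration-QTc model is assigned to the PK Analysis Set, which has no placebo participants, so its active-minus-placebo intercept cannot be estimated

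*SAP*

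**What the plan says.** SAP Section 10 lists the model output as "Linear Mixed-Effects Model for Plasma PK Concentrations of LY3885125 and ΔQTcF, Part A – PK Analysis Set" and its companion Figure 14.3.7.1 as "Scatter Plot of PK Concentration vs. QTcF – PK Analysis Set". SAP Section 5.1.5 defines that set as "All participants who have received at least one dose of LY3885125 and have sufficient concentration-time data to estimate PK parameters". Protocol Section 9.2 gives the same definition, and neither document makes an exception for placebo.

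The model text in SAP Section 5.11.6 is written for both arms. It takes "study treatment (active = 1 or placebo = 0) and time (i.e., post-dose time point: categorical) as fixed effects", states that "In all calculations, concentrations in participants who received placebo will be set to zero", and requires that "the treatment effect-specific intercept (defined as the difference between active and placebo) will be estimated together with the 2-sided 90% CI". The example code fits treatment (PRTAN) as a numeric variable listed first, then concentration, categorical time (AVISTPT) and baseline, with the NOINT option.

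Section 5.11, which contains Section 5.11.6, puts the safety analyses on the Safety Analysis Set, meaning everyone exposed to study intervention. Section 5.11.6 itself names no analysis set. The neighbouring ECG outputs (Tables 14.3.4.6.1 to 14.3.4.6.3) are titled with the Safety Analysis Set.

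**The concern.** The output title fixes the population for the analysis, and the population it names contains only one of the two arms the model compares. Protocol Section 9.3.6 commits to a concentration-response analysis of QT, and this is the only model-based cardiac safety analysis in the SAP. It has two headline estimates with confidence intervals: the concentration slope and the active-placebo intercept. If the title is followed, the second cannot be obtained. Any placebo-corrected prediction that relies on that intercept is lost with it. A program may also return a number under the treatment label without an error.

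**Working it through.** **How many participants are affected.** The ratios in protocol Section 4.1.1 and SAP Section 4 are 6:2 in Cohorts 1 and 2 and 9:2 in Cohorts 3 to 5.

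- Active: 2 × 6 + 3 × 9 = 39.
- Placebo: 2 × 2 + 3 × 2 = 10.
- Total: 39 + 10 = 49.
- Check that the ratios are head counts: 49 plus the 19 planned for Cohort 6 is 68, the Part A total in protocol Section 9.5.

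Cohort 6 was not enrolled (SAP Section 3). The PK Analysis Set therefore removes all 10 placebo participants, leaving at most 39.

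**Why the intercept is lost.** Write the fixed part of the model for participant i at time j as

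E(ΔQTcF) = θ·T_i + β·C_ij + τ_j + γ·B_i,

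where T is treatment (1 or 0), C concentration, τ_j the effect of time j, and B baseline QTcF, with no overall intercept.

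- With active participants only, T = 1 in every row. The time indicators also sum to 1 in every row, so the treatment column equals their sum.
- Replacing θ by θ + k and every τ_j by τ_j − k leaves all fitted values unchanged for any k. Only the sums θ + τ_j are identified, so θ is not. The individual time effects, which Section 5.11.6 also wants reported, are not identified either; only their differences are.
- With placebo rows (T = 0, C = 0), the expectation is τ_j + γ·B_i. This fixes each τ_j, and therefore θ.

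The argument does not depend on how many ECG times there are or on the concentrations, both of which are redacted.

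**Numerical check.** The fixed-effects matrix was built with 6 assumed time points and illustrative concentrations, giving 1 + 1 + 6 + 1 = 9 columns.

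| Population | Columns | Rank | Active-placebo intercept | Slope |
|---|---|---|---|---|
| PK Analysis Set (39 active) | 9 | 8 | not estimable | estimable |
| Safety Analysis Set (39 active + 10 placebo) | 9 | 9 | estimable | estimable |

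**What might be printed.** If software resolves the redundancy by setting the last time level to zero, which is likely with treatment listed first, the coefficient labelled treatment estimates θ + τ_last. A least-squares simulation illustrates this. It used 500 replicates, a true θ of 0 ms, a true slope of 0, time effects of −4, −2, 0, 2, 3 and 5 ms, between-participant and residual SDs of 5 ms each, and centred baseline.

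- Active only, last time level removed: the treatment coefficient averaged 4.98 ms against an expected 0 + 5 = 5 ms.
- With placebo: it averaged 0.05 ms (SD across replicates 2.06).
- Slope: it averaged −0.008 (SD 0.174) active only and −0.002 (SD 0.183) with placebo, both close to the true 0.

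Least squares is enough here, because the aliasing belongs to the fixed-effects design and not to the random effects. The 5 ms is an assumed time effect, not a prediction for this trial.

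**The case against.** The best defence is that this is a slip in a title and the intent is plain. The model text includes placebo throughout, and Section 5.11 points to the Safety Analysis Set. Section 10 has other slips: the overall adverse event table is on the Full Analysis Set, one table number begins with 13, and medications are at ATC Level 3 against Level 2 in Section 5.8. The model table is also assigned independent programming by a statistician, and a zeroed last time level would be visible among the reported time effects.

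The intent is indeed plain, and the other ECG outputs are unaffected. But the title and set definition are explicit programming instructions, and the SAP does vary the set by output on purpose: Section 5.9.1 uses the PK set for concentration tabulations and the Safety set for listings. Two programmers applying the same named set would agree with each other. Unlike a wrong table number, this label changes what can be estimated.

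On the figure, a scatter plot of dosed participants alone is defensible, since five dose levels still give distinct treatment groups. The case for changing it is consistency with the model.

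A reader might go further and infer that the slope becomes confounded with time of day. The documents do not support that: time is a categorical fixed effect, and several dose levels give different concentrations at the same time point.

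A reader might also infer from the convergence rule, under which "the random effect on the slope and intercept will be dropped, in this order, until convergence is achieved", that confidence limits will be too narrow. Repeated ECGs are treated as independent only if the random-slope model fails and the random-intercept model then fails too. The second failure is unlikely when between-participant variation is large enough to matter, and dropping the term does little harm when that variation is near zero. The documents give no variances from which to size the effect.

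Finally, the lack of a predicted QTcF effect at Cmax is a gap that could usefully be filled, but it contradicts nothing in the documents.

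**Conclusion.** The SAP is wrong as written on one specific point. Table 14.3.4.9 places the model on a set with 0 of about 10 planned placebo participants, so the active-minus-placebo intercept required by Section 5.11.6 cannot be estimated. That follows from the set definition and the model form alone. The count of 10 assumes the ratios are head counts, which the total of 68 supports.

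The slope survives, but its time effects are then estimated without placebo. That a misleading treatment coefficient would be printed is an inference from the order of the model terms. This is a population-label error that changes a result, not evidence that the model itself is unsound.

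**What to change.** Assign Table 14.3.4.9 and Figure 14.3.7.1 to the Safety Analysis Set. Alternatively, define a QTc set: Safety Analysis Set participants, active and placebo, with a baseline and at least one post-dose QTcF, using time-matched concentrations for active and 0 for placebo. Add the chosen set to Section 5.11.6, which at present names none. A dedicated set also avoids losing active participants whose data are too sparse for PK parameters but usable in this model.

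The cost is a few lines in the SAP and table shells, with no new data. Section 5 requires these to be approved before the Part A database lock; a later change would need an addendum.

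Two optional improvements could be made in the same edit. First, end the convergence fallback at the random-intercept model, or use a compound-symmetric structure or sandwich variance if that fails. Second, pre-specify the predicted placebo-corrected change in QTcF, with its 90% CI, at the geometric mean Cmax of each dose.
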